6.2. Laboratory Values

Laboratory values will be presented in standard units. For multiple values for a test at a visit from the same laboratory, the last non-missing value at that visit will be used.

Mean and mean change from baseline in clinical laboratory data will be summarized at each scheduled nominal visit by treatment group.

In addition, box plot of hematology and chemistry parameters will be presented by nominal visit and treatment group.

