The antitumor efficacy of unesbulin was evaluated in vivo in studies utilizing xenograft models of LMS. Unesbulin as a single agent and in combination with other standard-of-care anticancer agents, including DTIC, has demonstrated efficacy in rodent models of LMS. Notably, in a study where the efficacy of unesbulin was evaluated as monotherapy and in combination with DTIC using an SK-LMS-1 mouse model of LMS, the combination of unesbulin and DTIC was markedly more effective than either agent alone. The combination of unesbulin (through Day 98) and DTIC (21 mg/kg intraperitoneal once daily for 5 days) was highly effective in suppressing tumor growth. At Day 165 (when the study ended), tumors were not visible in 5 of the original 8 mice that received the combination treatment, whereas mice treated with unesbulin or DTIC alone showed progressive tumor growth.

Based on strong nonclinical data for the unesbulin and DTIC combination, along with an expected favorable toxicity profile for the combination, PTC initiated an ongoing, Phase 1b study of unesbulin in combination with DTIC for the treatment of unresectable or metastatic, relapsed or refractory LMS (Study PTC596-ONC-007-LMS). The primary objectives of the study are to determine the maximum tolerated dose, recommended Phase 2 dose (RP2D), and safety of unesbulin in combination with DTIC. Subjects are treated with unesbulin orally twice weekly (BIW) in combination with DTIC administered IV once every 21 days (Q21D).

Preliminary results for the 18 subjects exposed to the combination therapy of unesbulin at various dose levels with DTIC in Study PTC596-ONC-007-LMS demonstrated that the 300 mg BIW dose exhibited favorable efficacy and safety profiles with manageable toxicity compared with the 400 and 200 mg dose levels. Most cases of Grade 3-4 neutropenia and thrombocytopenia resolved within days without the need for treatment discontinuation or administration of growth factors or immunostimulants.

Together with the available nonclinical and PK data from the unesbulin clinical studies, PTC considers the dose of 300 mg unesbulin BIW in combination with DTIC to be the appropriate RP2D.

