- At the time when DTIC is reintroduced, clinical laboratory (ie, CBC and CMP) and body weight assessments must be performed within 24 hours prior to DTIC reintroduction. A single ECG must also be performed approximately 2 hours after reintroduction of DTIC if the interruption occurs within the first 3 treatment cycles. If DTIC is interrupted or held

in Cycle 3, then the same intensive PK sampling schedule for DTIC and unesbulin/placebo should be followed in the subsequent cycle as described in footnote "n" of the Schedule of Assessments.

For instructions for managing hematological and nonhematological toxicities, refer to Table 2 and Table 3, respectively.

Table 2:	Interventions for Common Hematological Toxicities by Grade
----------	--

Toxicity Grade	DTIC Intervention
Neutropenia	
Grade 1 (ANC <1500/mm ³ to <lln)< td="">Maintain same dose.	</lln)<>	Maintain same dose.
Grade 2 (ANC 1000/mm ³ to <1500/mm ³)	Maintain same dose.
Grade 3 (ANC 500 to <1000/mm ³)	Hold DTIC until resolved to ≤Grade 2, then:
	If resolved ≤7 days, resume at original dose level.
	If resolved >7 days or second or subsequent
	occurrence, resume DTIC at one dose level lower.
	Consider addition of colony-stimulating factor (eg,
	pegfilgrastim) if not already employed.
Grade 4 (ANC <500/mm ³ or febrile	Hold DTIC until resolved to ≤Grade 2, then restart at
neutropenia)	one dose level lower.
	Consider addition of colony-stimulating factor (eg,
	pegfilgrastim) if not already employed.
Thrombocytopenia	
Grade 1 (PLT 75000 to <lln)< td="">Maintain same dose.	</lln)<>	Maintain same dose.
Grade 2 (PLT 50000 to <75000)	Hold DTIC until resolved to ≤Grade 1, then:
	If resolved ≤7 days, resume at original dose level.
	If resolved >7 days or second or subsequent
	occurrence, resume DTIC at one dose level lower.
Grade 3 (PLT 25000 to <50000)	Hold DTIC until resolved to ≤Grade 1, then restart at
Grade 4 (PLT <25000) or thrombocytopenia	one dose level lower.
with clinically significant bleeding	

Abbreviations: ANC, absolute neutrophil count; DTIC, dacarbazine; LLN, lower limit of normal; PLT, platelets

 Table 3:
 Interventions for Nonhematological Toxicities by Grade

Toxicity Grade	DTIC Intervention
Grade 1 or 2	Maintain same dose.
Grade 3 or 4	Hold treatment until Grade ≤2, then restart at one dose
Manageable with supportive care	level lower.
Grade 3 or 4	Hold treatment until Grade ≤2, then restart at one dose
Not manageable with supportive care	level lower.

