8.4.5. Safety Analyses

The safety analysis will be performed for all treated subjects. Descriptive statistics of safety will be presented using NCI CTCAE V5.0 by treatment group. All TEAEs will be tabulated by system organ class and MedDRA preferred term. On-study laboratory abnormalities including hematology and chemistry will be summarized using worst grade per NCI CTCAE V5.0 criteria.

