8.4.5.2. Laboratory Abnormalities

The severity of laboratory abnormalities will be graded using the NCI CTCAE V5.0 whenever possible. The frequency of subjects experiencing a specific laboratory abnormality will be tabulated by treatment group and worst severity. In addition, the number and percentage of subjects experiencing a specific laboratory abnormality will be tabulated similarly.

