3. GENERAL CONSIDERATIONS

3.1. General Considerations

Continuous data will be summarized using number of observations (n), arithmetic mean (mean), standard deviation, median, minimum value (min) and maximum value (max) by treatment group. Categorical variables will be summarized using the frequency count (n) and percentage (%) by treatment group. An overall/total group (i.e., sum of all treatment groups) will generally be presented additionally for summaries of disposition, demography, and baseline characteristics.

For all percentage calculations, the denominator will be the number of subjects in the analysis set for the treatment group, unless otherwise stated.

Only data from protocol scheduled visits will be included in the summary tables. Data from unscheduled visits will not be included in the summary tables but will be included in the by-subject listings. Descriptive summaries by visit and treatment will be provided for all the primary and secondary efficacy endpoints.

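### The SAP's laboratory rules do not secure the protocol's worst-grade table: SAP 6.2 keeps the last value at a visit and lists no such table, and SAP 3.1 leaves out unscheduled values

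*SAP*

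**What the plan says.** SAP 6.2 opens with a selection rule for laboratory data: "For multiple values for a test at a visit from the same laboratory, the last non-missing value at that visit will be used". It does not tie the rule to particular outputs. The outputs it then lists are descriptive and by visit: "Mean and mean change from baseline in clinical laboratory data will be summarized at each scheduled nominal visit by treatment group", and a "box plot of hematology and chemistry parameters will be presented by nominal visit and treatment group". No graded or worst-value table appears.

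SAP 3.1 adds a rule for all summaries: "Data from unscheduled visits will not be included in the summary tables but will be included in the by-subject listings".

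The protocol asks for something different. Section 8.4.5 says: "On-study laboratory abnormalities including hematology and chemistry will be summarized using worst grade per NCI CTCAE V5.0 criteria". Section 8.4.5.2 repeats it as a table: "The frequency of subjects experiencing a specific laboratory abnormality will be tabulated by treatment group and worst severity". SAP 3.7 reports no departure from the protocol's safety analyses, so that table is still owed.

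**The concern.** Repeat blood counts are not taken at random. For Grade 3 neutropenia, Table 2 in Protocol 3.3 says "Hold DTIC until resolved to ≤Grade 2, then", followed by instructions for resuming, and counts must be rechecked within 24 hours before DTIC restarts. A low count therefore tends to lead to a repeat, and a normal count does not. On the Phase 1b experience, Protocol 1.2 reports: "Most cases of Grade 3-4 neutropenia and thrombocytopenia resolved within days without the need for treatment discontinuation". When a later value falls at the same visit, it may well be a recovered one.

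Under the rule in SAP 6.2 the recovered value would displace the low count that prompted the repeat. A low count found only at an unscheduled visit would be removed by SAP 3.1. A worst-grade table exists to show exactly those values. Protocol 1.3 names myelosuppression as the most common source of treatment-related Grade 3 or 4 events, so at stake is whether the laboratory tables describe that toxicity as the protocol intended.

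**Working it through.** The documents give no figure to reproduce on this point: no rate of low counts, no repeat rate and no comparison of cytopenias between arms. The check is therefore a comparison of rules, followed by an illustration on assumed inputs.

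**Step 1. Which value survives?** The middle column applies SAP 6.2 and SAP 3.1 together. The right column is a worst-grade derivation from all post-baseline values.

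| Low count | Later value | Kept under the SAP rules | Kept when all values are used |
|---|---|---|---|
| Scheduled visit | Recovered; same visit and laboratory | Recovered value | Low count |
| Scheduled visit | Recovered; filed as unscheduled | Low count | Low count |
| Scheduled visit | Lower still; same visit and laboratory | Lower value | Lower value |
| Scheduled visit | Lower still; filed as unscheduled | First, less extreme value | Lower value |
| Unscheduled visit only | Any | Low count not kept | Low count |

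The SAP rules lose the most extreme value in rows 1, 4 and 5. They do no harm in rows 2 and 3.

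**Step 2. Can these rows arise?** Days 1, 8 and 15 have a window of ±2 business days, and from Cycle 2 laboratory samples may be drawn up to 48 hours before dosing (Protocol Table 1, footnotes b and g). Two draws at one nominal visit are therefore possible. After Cycle 3 the scheduled laboratory tests fall to once per cycle (footnote g), so a mid-cycle low would usually be seen only on an extra draw. The documents do not say under which visit a repeat laboratory test is filed.

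**Step 3. Illustration for a table of Grade 3-4 counts at one visit.** Let q be the share of an arm with such a count, and r the share of those with a recovered value at the same visit and laboratory. Then

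share shown = q × (1 − r), and share lost = q × r.

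With assumed q of 30% (unesbulin) and 10% (placebo), and the same r in both arms:

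| r | Shown, unesbulin | Shown, placebo | Difference (points) | Ratio |
|---|---|---|---|---|
| 0 | 30.0% | 10.0% | 20 | 3.0 |
| 0.25 | 22.5% | 7.5% | 15 | 3.0 |
| 0.50 | 15.0% | 5.0% | 10 | 3.0 |
| 0.75 | 7.5% | 2.5% | 5 | 3.0 |

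With equal r the absolute difference shrinks by the factor (1 − r) and the ratio does not move. With equal q (20% in each arm) and r = 0.50, both arms lose 10 points and the difference stays at zero. If r differs between arms, the ratio can move either way:

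- r = 0.50 on unesbulin and 0.25 on placebo gives 15% vs 7.5%, a ratio of 2.0.
- r = 0.25 on unesbulin and 0.50 on placebo gives 22.5% vs 5%, a ratio of 4.5.

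In a table of worst grade over the whole study, a subject is misgraded only if every value at that grade is lost, so the per-visit figures do not carry over directly.

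**Step 4. Illustration for the outputs the SAP does list.** Shift in a visit mean = q × r × (recovered value − low value). Assume neutrophils recover from 750 to 1500/mm³, with q and r as above:

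- Unesbulin: 0.30 × 0.25 × 750 = 56 to 0.30 × 0.75 × 750 = 169/mm³.
- Placebo: 0.10 × 0.25 × 750 = 19 to 0.10 × 0.75 × 750 = 56/mm³.

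Every q, r and count in Steps 3 and 4 is an assumption. If r = 0, the same-visit effect is nil.

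**The case against.** The strongest case against has five parts.

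- **The adverse event tables already show the toxicity.** SAP 6.1 tabulates events by maximum severity and at Grade 3 or higher, and Protocol 7.3.7 asks for the highest grade of each episode. A count that causes DTIC to be held plausibly qualifies as an adverse event. This stands in large part. It is not complete cover: under Protocol 7.3.1, an abnormality that leads only to a confirmatory repeat need not be reported as an event.
- **The mechanism is narrow.** It needs the same visit and the same laboratory. Protocol Table 1 (footnote i) sends the ECG after a DTIC interruption to an unscheduled form page; if laboratory repeats are handled likewise, a low count at a scheduled visit stays in. DTIC is planned for Day 1 only, Table 2 uses a 7-day cut-off for recovery, and resolution within days need not mean within a visit window. All of this stands and limits the same-visit route. It does not touch the exclusion of unscheduled lows.
- **No document says the last-value rule would be applied before grading.** True, but nothing says it would not, and the rule precedes all laboratory outputs without restriction.
- **The worst-grade table may be in the separate table shells.** SAP sections 1 and 8 place the specifications elsewhere, so it may be. The SAP would still not say which values feed it.
- **The outputs are descriptive, and the SAP itself records the futility recommendation.** Correct: no test, efficacy result or error rate depends on this.

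A reader might infer that the rule is already known to understate myelosuppression, and most in the arm with more of it. The documents do not support that. They give no rates by arm and no comparison with DTIC alone. A larger loss in one arm follows on the absolute scale only if that arm has more low counts and repeats recover equally often, and the ratio is then unchanged. A reader might also conclude that by-visit means should use the first value instead of the last. That is a choice of convention: the first value misses a count that is still falling, which the last value keeps.

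**Conclusion.** The point holds as a mismatch between the documents. The protocol requires a worst-grade laboratory table by treatment group and SAP 3.7 says nothing has changed. SAP 6.2 nevertheless does not list that table, and the rules in SAP 6.2 and SAP 3.1, taken literally, can remove the values it should contain. When a recovered same-visit repeat is kept, or a low count seen only off schedule is dropped, the error runs towards less apparent myelosuppression.

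The size cannot be estimated. It depends on where repeats are filed, how often they show recovery and how many of the lowest counts are unscheduled, none of which is given. The same-visit part is zero if recovered repeats are filed as unscheduled and the low values were at scheduled visits. It would not be right to say that the sponsor dropped the table, since the shells are separate and SAP 3.7 declares no change. This is a specification gap in descriptive safety reporting, worth closing because the correction costs little.

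**What to change.** Amend SAP 6.2 in two places:

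1. State that the last-value rule applies only to the by-visit means, mean changes and box plots.
2. List the protocol's table of laboratory abnormalities by worst CTCAE V5.0 grade and treatment group. Derive it from all post-baseline values, including same-visit repeats and unscheduled visits, and mark it as an exception to SAP 3.1.

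The by-visit outputs can stay as they are. If the sponsor does not intend to produce the worst-grade table, SAP 3.7 should record that as a change from the protocol.

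The cost is a short text change and a little more programming, with no new data collection and no effect on efficacy, alpha or power. The downside is that an occasional faulty sample would count towards the worst grade unless it is flagged as invalid.

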BOR will be summarized by response category for each treatment group. ORR will be computed in each treatment group along with the exact 95% CI using Clopper-Pearson method. An estimate of the difference in ORRs and corresponding 95% CI will be calculated using Cochran-Mantel-Haenszel methodology and adjusted by the same stratification factors as in primary analysis of PFS.

For subjects with at least 4 prior lines of treatment, a sensitivity analysis will be performed to explore the efficacy for this population.

PK: PK of unesbulin, DTIC, and AIC will be analyzed using standard compartmental or noncompartmental analysis methods, as appropriate for the data. The impact of unesbulin on the PK of DTIC and AIC will be investigated.

Safety: The safety analysis will be performed for all treated subjects. Descriptive statistics of safety will be presented using National Cancer Institute (NCI) Common Terminology Criteria for Adverse Events Version 5.0 (CTCAE V5.0) by treatment group. All treatment-emergent AEs will be tabulated by system organ class and Medical Dictionary for Regulatory Affairs (MedDRA) preferred term. Laboratory abnormalities, including hematology and chemistry, will be summarized using worst grade per NCI CTCAE V5.0 criteria.

SCHEDULE OF ASSESSMENTS

Table 1:	Schedule of Study	Assessments and Procedures
----------	-------------------	----------------------------

Assessment	Screening								Cycle 2									С	ycle	3 +			EOT ^a	FUP ^a	sFUP ^a
Study Week		1			2		3		1			2		3		1			2		3				
Cycle Day	-28 to -1	1	2	5	8	11	15	18	1	2	5	8	11	15	18	1	2	5	8	11	15	18			
Time Window ^b	-	2	1	1	2	1	2	1	2	1	1	2	1	2	1	2	1	1	2	1	2	1	1	3	3
Informed consent	Х																								
Eligibility	Х																								
Medical history	Х																								
Con. meds ^c	Х											Throu	ghout	stud	y									Х	
Pathology review ^d	Х																								
Physical exam ^e	Х	Х							Х							Х							Х		
Height	Х																								
Weight ^f	Х	Х							Х							Х							Х		
Vital signs	Х	Х							Х							Х							Х		
ECOG PS	Х	Х							Х							Х							Х		
Adverse events	Х										٦	Throu	ghout	stud	у									Х	
Laboratory tests ^g	Х	Х			Х		Х		Х			Х		Х		Х			Х		Х		Х		
HIV, hepatitis	Х																								
serologies																									
Urine/serum	Х	X ^h							X ^h							X ^h									
pregnancy test ^h																									
Urinalysis	Х																						Х		
ECG (single) for	Х	Х							Х							Х							Х		

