1.2. Study Objectives and Endpoints

Table 1:Study Objectives and Endpoints

Objectives	Endpoints
Primary Objective: PFS of unesbulin plus DTIC versus placebo plus DTIC	Primary Endpoint: PFS per RECIST 1.1 assessed by an independent central imaging laboratory.
Key Secondary Objective: Efficacy : OS of subjects treated with unesbulin plus DTIC versus placebo plus DTIC	Key Secondary Endpoint: Efficacy: OS
Other Secondary Objectives: Efficacy : Antitumor activity of unesbulin plus DTIC versus placebo plus DTIC	 Other Secondary Endpoints: Efficacy: ORR (proportion of subjects with BOR of either CR or PR) DCR or CBR, defined as the proportion of subjects with BOR of CR, PR, or at least 3 months of SD DoR
Safety : Safety and tolerability of unesbulin plus DTIC versus placebo plus DTIC	Safety : Vital signs, physical examination, ECG, laboratory abnormalities, ECOG PS scores, and AEs
Exploratory Objectives: Efficacy : Evaluate the antitumor activity of unesbulin plus DTIC versus placebo plus DTIC in subjects with at least 4 prior lines of treatment.	Exploratory Endpoints : Efficacy : PFS, OS, ORR, DCR, and DoR in subjects with at least 4 prior lines of treatment.
 PK: Evaluate the PK of unesbulin in the presence of DTIC in subjects with LMS Evaluate the PK of DTIC/AIC alone and in the presence of unesbulin in subjects with LMS. 	 PK parameters of unesbulin in subjects who receive unesbulin plus DTIC: C_{max}, T_{max}, and AUC_{0-t} PK parameters of DTIC and its inactive metabolite AIC in subjects who receive

Objectives	Endpoints
	unesbulin plus DTIC and placebo plus DTIC: Cmax, Tmax, and AUC _{0-t} .
PROs : Compare the effect of unesbulin plus DTIC versus placebo plus DTIC on PROs, including HRQoL assessments.	PROs: 30-item score EORTC QLQ-C30 and EQ-5D-5L
Biomarkers : Measure genotype of subject tumors, assessed by blood sampling, at baseline and posttreatment	Biomarkers : Genetic evaluation of the tumors by analyzing ccfDNA

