3.7. Changes to Protocol Specified Analysis

There are no changes in the protocol-specified analyses of efficacy (primary, secondary, and exploratory), safety, and PK endpoints. Exploratory analyses for the patient-reported outcomes and biomarkers will not be performed due to futility of the primary efficacy endpoint.

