6.4. ECOG Performance Status

ECOG performance status (PS) will be summarized at baseline and shift from baseline to worst level during the treatment phase. A supporting list will also be provided.

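### SAP Section 6.2 does not specify the worst-grade laboratory tables that the protocol requires, and SAP Section 3.7 does not declare their removal

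*SAP*

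**What the plan says.** The protocol states the laboratory analysis three times.

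- Synopsis, Statistical Methods (Safety): "Laboratory abnormalities, including hematology and chemistry, will be summarized using worst grade per NCI CTCAE V5.0 criteria".
- Section 8.4.5: "On-study laboratory abnormalities including hematology and chemistry will be summarized using worst grade per NCI CTCAE V5.0 criteria".
- Section 8.4.5.2: "The frequency of subjects experiencing a specific laboratory abnormality will be tabulated by treatment group and worst severity". The same section also asks for numbers and percentages of subjects.

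SAP Section 1.2, Table 1, carries the endpoint forward among the safety endpoints: "Vital signs, physical examination, ECG, laboratory abnormalities, ECOG PS scores, and AEs".

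SAP Section 6.2 then plans three outputs. Two are in one sentence: "Mean and mean change from baseline in clinical laboratory data will be summarized at each scheduled nominal visit by treatment group". The third is box plots of hematology and chemistry by nominal visit and group. Where a test has several values at one visit from the same laboratory, the last non-missing one is taken.

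SAP Section 3.1 restricts summary tables to scheduled visits and sends unscheduled-visit data to the by-subject listings.

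SAP Section 3.7 declares what changed from the protocol: "There are no changes in the protocol-specified analyses of efficacy (primary, secondary, and exploratory), safety, and PK endpoints". The analyses that it names as dropped are these: "Exploratory analyses for the patient-reported outcomes and biomarkers will not be performed due to futility of the primary efficacy endpoint".

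**The concern.** A mean or a box plot at a visit does not show how many subjects ever reached a given grade. The protocol's table answers that question, and it matters here. Protocol Section 1.3 names myelosuppression as the source of the most common treatment-related Grade 3 or 4 events with the combination, and protocol Table 2 ties DTIC holds and reductions to neutrophil and platelet grade.

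As the SAP text stands, an analyst who follows it produces no count of subjects by worst laboratory grade in either arm. A reader of SAP Section 3.7 is nevertheless told that the safety analyses are as the protocol has them. Either Section 6.2 is incomplete or Section 3.7 is inaccurate.

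A second issue arises if the table is produced from the separate shells. The SAP's general data-handling rules are suited to by-visit means. Applied to a worst-value summary, they discard some of the values that define the worst.

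**Working it through.** The plan gives no figure to reproduce. The check is a comparison of texts, followed by one argument about direction.

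**1. Protocol commitment against SAP outputs**

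| Protocol element | SAP Section 6.2 |
|---|---|
| Grading by CTCAE V5.0 | Not mentioned |
| Worst value per subject | Not mentioned |
| Number and percentage of subjects by grade | Not mentioned |
| By treatment group | Yes, but for means, mean changes and box plots |

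The commitment appears in 3 places in the protocol. Of the 3 outputs in SAP Section 6.2, 0 count subjects by grade. No other SAP section grades laboratory values: the severity tables in SAP Section 6.1 are for treatment-emergent adverse events.

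**2. Does the SAP leave such detail out as a matter of style?** No. It states worst or maximum summaries for other safety domains: adverse events by maximum severity (Section 6.1), maximum QTc (Section 6.5) and performance status, where "ECOG performance status (PS) will be summarized at baseline and shift from baseline to worst level during the treatment phase". The laboratory section is the one that lacks this.

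**3. Is the absence declared?** No. Section 3.7 names only the patient-reported outcome and biomarker analyses as not performed.

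**4. Effect of the general rules on a worst-grade table, if one is produced**

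- Let A be all of a subject's post-baseline grades for a test, and let K be those kept after the scheduled-visit rule (SAP Section 3.1) and the last-value rule (SAP Section 6.2).
- K is a subset of A, so max(K) ≤ max(A).
- The number of subjects at or above any grade can therefore stay the same or fall. It cannot rise.
- Example with the bands in protocol Table 2: a neutrophil count in the Grade 3 band (500 to below 1000/mm³), followed at the same visit and laboratory by a repeat in the Grade 2 band (1000 to below 1500/mm³), enters as Grade 2.

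The size of the shortfall cannot be computed. The documents do not give the number of repeat or unscheduled laboratory values, overall or by arm.

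**5. What the other planned outputs still capture**

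- Protocol Section 7.3.1 makes an abnormality an adverse event if it needs intervention or further investigation beyond a repeat test, unless it belongs to a clinical event already reported.
- Protocol Section 7.2.1 says Grade 3 and 4 abnormalities should in general be considered clinically significant.
- SAP Section 6.1 tabulates adverse events by maximum severity and those of Grade 3 or higher. SAP Section 4.9 summarizes missed and reduced doses with reasons.
- Without any summary are mainly lower-grade abnormalities that were not acted on, which protocol Section 7.3.1 keeps out of adverse event reporting. In protocol Table 2, Grade 1 and 2 neutropenia and Grade 1 thrombocytopenia call for no change in DTIC, so they could fall in this group.

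**The case against.** The strongest reply is that silence is not removal. If Section 3.7 says the safety analyses are unchanged, then protocol Sections 8.4.5 and 8.4.5.2 remain in force, and Section 6.2 simply does not repeat them. SAP Sections 1 and 8 place table specifications in a separate document, which may include the graded table. This stands in part. A reader might infer that the sponsor dropped the analysis, or that the table will not be produced; the documents show neither. They show that the SAP text does not specify the table, does not point to the shells or the protocol for it, and gives no rule for selecting the worst value.

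A second reply is that specific wording in this SAP already prevails over the general rule in Section 3.1. Overall survival uses the last record of any kind (Section 5.2.1), best overall response uses all available assessments (Section 5.3.1.1), and performance status uses the worst level on treatment (Section 6.4). This is a fair reading of those sections, but it does not help the laboratory data, because Section 6.2 has no such wording.

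The second reply does bear on ECGs. The protocol requires an ECG after DTIC is reintroduced if the interruption falls in the first 3 cycles, and footnote i of protocol Table 1, for subjects outside the PK assessment, puts it on an unscheduled form page. A reader might infer that maximum QTc will be understated. The documents do not establish this: a form page is not necessarily a visit, the ECG is itself required by the protocol, and SAP Section 6.5 refers to every post-dose time point, which may already include it. That is a matter for clarification only.

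A third reply is that the loss is small, because acted-on abnormalities reach the adverse event tables and unscheduled values are listed. This stands and limits the weight of the point. It does not remove it: the criterion for an adverse event is need for action, not grade, and the protocol promised graded laboratory tables in addition to adverse event tables.

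**Conclusion.** The point holds as a mismatch between protocol and SAP. The protocol requires laboratory abnormalities by worst CTCAE V5.0 grade and treatment group; the SAP text does not specify that analysis and does not declare its removal. If the table is made under the SAP's general rules, any error in worst grade is downward.

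The size is limited and cannot be expressed as a number from the documents. It concerns the completeness of the safety report, mainly for lower-grade abnormalities that were not acted on. SAP Section 3.5 records that the data monitoring committee recommended stopping for futility, so no efficacy claim depends on it. The correction should be made, but nothing else in the plan turns on it.

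The conclusion rests on the SAP text alone. If the shells contain a worst-grade table built on all post-baseline values, what remains is a missing statement in the SAP.

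**What to change.** - **SAP Section 6.2:** add the number and percentage of subjects by worst post-baseline CTCAE V5.0 grade, by test and treatment group, using all on-study values including unscheduled and repeat ones. Keep the last-value rule for by-visit means only.
- **Or SAP Section 3.7:** if the graded tables were left out on purpose, declare this and give the reason.
- **SAP Section 3.1:** limit the scheduled-visit restriction to by-visit summaries.
- **SAP Section 6.5 (clarification only):** state that overall maximum-QTc summaries include the protocol-required ECG after DTIC reintroduction, including where it is recorded on an unscheduled form page.

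The cost is a few sentences in the SAP and a few standard tables from data already collected. No new assessments are needed.
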